9.2 Analysis of Primary Endpoint

Aim 1: Multivariate linear regression models will be used to analyze the effects of baseline PSG-derived standard measures of sleep disordered breathing (including RDI, ODI, minimum O2 saturation), on individual cognitive test scores (continuous outcome variables of interest, in separate models) for Aim 1, controlling for other sleep, serological, and clinical variables. Additional models that use computed respiratory cycle-related EEG changes (calculated as the maximum difference between the mean EEG powers associated with each of the 4 respiratory cycle segments as predictor variables) will be used to evaluate the effects of respiratory-related cortical microarousals on cognitive test scores, controlling for other clinical and sleep-related variables. Separate models that use computed temporal patterns of sleep stages as predictors of cognitive test scores will also be constructed.

Aim 2: Multivariate linear regression models will be used to test the effects of Group effect on 3-month (“post”) cognitive test scores, controlling for baseline (“pre”) test scores. We will also examine the association of PAP use as a continuous variable, based on mean nightly hours of use per month, on 3-month individual cognitive test scores, controlling for baseline scores. Separate models will be used for each cognitive test of interest. Predictor variables that are unbalanced between groups despite randomization will be used as covariates in the analyses.

To evaluate early effects of PAP therapy on cognitive scores, sleep stage dynamics will also be assessed during PAP titrations to determine whether changes in sleep stage stability predict improvements on cognitive test scores in separate models.

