Analyses will focus on relationships between standard PSG measures (Respiratory Disturbance Index, oxygen desaturation index, and minimum oxygen saturation), innovative new quantitative PSG measures and cognitive test scores, as well as mean changes from baseline in individual cognitive scores following treatment with PAP therapy.

For aim 1, multivariate linear regression models will be used to analyze the effects of PSG-derived standard measures of sleep disordered breathing (including RDI, ODI, minimum O2 saturation), on individual cognitive test scores (continuous outcome variables of interest, in separate models). For Aim 2, multivariate linear regression models will be used to test the effects of Group effect on 3-month (“post”) cognitive test scores, controlling for baseline (“pre”) test scores and other covariates. We will also examine the association of PAP use as a continuous variable, based on mean nightly hours of use per month, on 3-month individual cognitive test scores, controlling for baseline scores.

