Furthermore, preliminary findings from the investigators suggest that sleep disturbances, and OSA in particular, could contribute to domains of cognitive dysfunction that are key aspects of morbidity in MS. If a causal role does exist, identification and treatment of OSA could provide new opportunities to improve cognition in MS patients. **This study will for the first time prospectively evaluate the effects of OSA severity and its treatment on multiple key domains of cognitive function most affected in patients with MS, while controlling for other sleep- and MS-related variables that may influence these relationships.**

Hypotheses

Hypothesis 1: Sleep apnea severity, as reflected by standard PSG measures [respiratory disturbance index (RDI), oxygen desaturation index (ODI), and minimum oxygen saturation (Min O₂)], as well as innovative new quantitative approaches, will be associated with reduced MACFIMS scores.

Hypothesis 2: Group 1, in comparison to Group 2, will show greater improvement from baseline in MACFIMS scores, on repeat MACFIMS testing at month 3.

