4.2 Exclusion Criteria

- 1) Physical, psychiatric or cognitive impairment that prevents informed consent, PSG, PAP use, or reliable longitudinal follow-up
- 2) Cardiopulmonary conditions that may increase sleep apnea risk
- 3) Current treatment, such as PAP, for obstructive or central sleep apnea
- 4) History of surgical treatment for OSA
- 5) Nervous system diseases other than MS that may predispose subjects to OSA (such as Parkinson's disease, amyotrophic lateral sclerosis, or recent stroke)
- 6) History of concomitant central nervous system disease that could influence cognition, such as large vessel territory stroke, Alzheimer's disease, Parkinson's disease, or Lewy body dementia
- 7) Concomitant systemic autoimmune disease with secondary central nervous system involvement (including CNS lupus or neurosarcoidosis).
- 8) Pregnancy
- 9) Evidence of clinical MS relapse within the last 30 days prior to enrollment
- 10) Systemic high dose steroid use (1 gram IV methylprednisolone daily for 3-5 days or equivalent) for an MS relapse within the last 30 days prior to enrollment
- 11) Unwillingness to initiate PAP therapy if clinically indicated
- 12) Severe depression at screening per the Patient Health Questionnaire-8 (PHQ-8)
(The PHQ-8 is a brief, self-administered questionnaire that evaluates core symptoms associated with major depressive disorder. Scores range from 0 to 24 based on the frequency and severity of depressive symptoms over the previous two weeks.)
- 13) Anticipated initiation, dosage change, or discontinuation in medications that could, per the opinion of the investigators, influence cognitive test scores from baseline to follow-up, including MS disease modifying therapies, hypnotic agents, narcotic-based medications, benzodiazepines, antispasmodics, or 4-aminopyridine
- 14) ESS scores ≥ 16 on baseline visit
- 15) Subjects with extreme OSA accompanied by signs of cardiopulmonary compromise (RDI > 60 respiratory events per hour with severe nocturnal hypoxia or unstable ECG rhythms on PSG), will be excluded unless they are randomized to immediate PAP arm
- 16) Any other condition or treatment that in the opinion of the investigator could affect subject safety or study eligibility

Table 1: STOP-Bang questionnaire	
Snoring	Do you snore loudly (louder than talking or loud enough to be heard through closed doors)?
Tired	Do you often feel tired, fatigued, or sleepy during the daytime?

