5. STUDY TREATMENTS

5.1 Allocation to Treatment (see also 6.4)

Randomization Process: Subjects who meet all Inclusion/Exclusion criteria, including OSA on baseline or clinical PSG, will be randomized (2:1 randomization) to expedited PAP therapy (Group 1, n~93), or standard care PAP therapy (Group 2, n~47), after the subject has signed consent, completed the baseline activities, Randomization will be stratified by sleep apnea severity (RDI < or >=30) to minimize imbalances in apnea severity between groups.

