5.2 Blinding

PSG technicians, PSG interpreters, and study staff who conduct and score neuropsychological tests will remain blinded to group allocation for the duration of the study. **The subject, PI, co-investigators, coordinators, and statistician will not be blinded.**

5.3 Treatment with Positive Airway Pressure (PAP) Therapy: Unless already performed at U-M sleep lab within the past year, all subjects who are diagnosed with OSA on baseline or clinical PSG (n~140) will undergo PAP titrations* and be prescribed clinical PAP therapy by clinicians involved in the study or the subject's treating sleep provider. PAP therapy is considered standard clinical care for patients with obstructive sleep apnea. PAP is a mode of respiratory ventilation that blows air into the nose (or nose and mouth) to splint the upper airway open during sleep. PAP therapy can be delivered at a continuous pressure (CPAP), at different levels during inspiration and expiration (BiPAP), or at a range of auto-adjustable levels depending on the patient's breathing (AutoPAP)*. In order to determine which pressure setting most effectively treats an individual's sleep apnea, an overnight PAP titration study is typically required. This study is similar to a PSG in terms of overnight monitoring but also involves fitting of various masks which are then hooked up to the subject and PAP machine to test the effectiveness of various PAP settings, and to determine which mask/setting is most tolerable for the subject. PAP titration studies will be scored by certified PSG technologists and interpreted by a board-certified sleep physician, who will then place an order for PAP equipment at appropriate settings with a local durable medical equipment (DME) provider. DME will be covered by the subject's insurance.

* In some cases, insurance carriers will not cover the cost of an in-laboratory PAP titration, and instead will recommend an “auto-adjusting” PAP machine (also known as AutoPAP, or APAP) so that patients diagnosed with OSA may begin PAP without requiring a PAP titration.

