6.4 Randomization

Randomization Process/Blinding: Subjects who meet criteria for OSA on baseline or clinical PSG (n~140, anticipated) will be randomized (2:1 randomization) to determine whether they will receive expedited PAP therapy (Group 1, n~93), or standard of care PAP therapy (Group 2, n~47). Computer-based randomization will be stratified by sleep apnea severity (RDI $<$ or ≥ 30) to minimize imbalances in apnea severity between groups. PSG technicians, PSG interpreters, and study staff who conduct and score neuropsychological tests will remain blinded to group allocation for the duration of the study. The subject, PI, co-investigators, coordinators, and statistician will not be blinded. **Subjects will be contacted with the randomization**

assignment that determines whether they will be scheduled for immediate PAP titration (Group 1) or delayed PAP titration after their month 3 cognitive testing.

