13. STUDY DISCONTINUATION CRITERIA

Stopping Rules for Safety Reasons

Subjects who demonstrate evidence of severe excessive daytime sleepiness (as evidenced by ESS scores ≥ 16 at baseline) will result in exclusion from study. Subjects with extreme OSA that is accompanied by signs of cardiopulmonary compromise or severe nocturnal hypoxia on baseline PSG will also result in study exclusion unless they are randomized to expedited PAP arm. In such cases, subjects will be referred for expedited sleep clinic follow-up.

Discontinuation of a Subject

In the event a patient drops out of the study or is discontinued due to protocol violations, all attempts will be made to exit the patient in accordance with the protocol requirements.

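### Aim 2 covariates beyond the baseline score are triggered by observed imbalance, so RDI stratum, battery order and balanced prognostic factors are not assured a place in the model

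*Combined protocol and SAP*

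**What the plan says.** Section 9.2 (Aim 2) regresses each Month 3 test score on Group with the baseline score as covariate. It also fits models with mean nightly hours of PAP use as the predictor, again controlling for baseline. The same paragraph ends: "Predictor variables that are unbalanced between groups despite randomization will be used as covariates in the analyses". It does not define imbalance or list candidate variables.

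Other places bear on this:

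- The summary at the front (Statistical Methods) has the Group model control for baseline "test scores and other covariates", without naming any.
- Section 1.2 describes the study as "controlling for other sleep- and MS-related variables that may influence these relationships".
- Section 5.1: "Randomization will be stratified by sleep apnea severity (RDI < or >=30) to minimize imbalances in apnea severity between groups". Section 6.4 repeats the stratification.
- Section 6.2 randomises the order of test batteries A and B. Table 2 shows alternate forms for every repeated test except the NHPT and Go/No-go.
- Section 5.2: "The subject, PI, co-investigators, coordinators, and statistician will not be blinded".
- Section 9.1 bases its power for continuous PAP use on adjustment variables with an R-squared of at least 0.3, and does not name them.

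No Aim 2 model names the RDI stratum or battery order.

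**The concern.** In a randomised comparison, a covariate earns its place by predicting the outcome. Whether it happens to differ between groups says little about that. Screening on imbalance has three consequences here.

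1. The RDI stratum is balanced by design, so the screen tends to drop the factor that the design singled out.
2. Battery order is a design factor for the outcome measurement, and it would enter only by chance.
3. A variable that influences cognition but is balanced stays out, which sits badly with the aim stated in section 1.2.

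Because imbalance is undefined and allocation is known to the statistician, the final model is also open to choice.

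The PAP-hours model raises a different issue. Hours of use are not randomised. A comparison of Group 1 with Group 2 cannot show whether a variable is related to hours within Group 1, and that relation is what confounds the association.

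**Working it through.** **Plan's own figure.** Section 9.1 gives N = 140, 2:1 allocation (93 and 47), SD 9, two-sided 0.05 and a 5-point difference. SE = 9 × √(1/93 + 1/47) = 9 × 0.1790 = 1.611, and 5/1.611 = 3.104. Power = Φ(3.104 − 1.960) = 87.4% by the normal approximation, or 86.9% by noncentral t. The plan states 86.3%, so the figure reproduces and is not in dispute.

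**How often a screen admits a variable.** The plan gives no threshold, so p < 0.05 is assumed. An unrestricted covariate then enters in about 5% of trials. At least one of five enters in 1 − 0.95⁵ = 22.6% (about 22% simulated). With permuted blocks within RDI stratum, the stratum entered in 0% of simulated trials; without blocks, in 5%. The documents do not state blocking.

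**Effect on the standard error (all strengths assumed).** Let the baseline score explain half the variance: 81 × 0.5 = 40.5. In a strong case, the stratum is worth 3 points with 35% of subjects at RDI ≥30, order is worth ±2 points, and three further covariates have R² 0.02 each.

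- Stratum and order omitted: 40.5 + 3² × 0.35 × 0.65 + 2² = 46.55; SD 6.82; SE = 6.82 × 0.1790 = 1.22 (simulated under the screen 1.224).
- Stratum and order included: SD √40.5 = 6.36; SE 1.14 (simulated 1.147).
- All five included: 40.5 − 3 × 0.02 × 81 = 35.64; SD 5.97; SE 1.07 (simulated 1.088, after loss of degrees of freedom).

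Under the screen the estimate's actual SD was 1.172 against the reported 1.224, hence the conservatism. Type I error was 4.2% with blocks and 4.3% without.

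**Power** (20,000 trials per cell, blocks of 6, Monte Carlo SE about 0.3 points at 70%). The weak case halves the effects: stratum 1.5, order ±1, R² 0.01 each.

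| Assumed strength | Difference | Screen | Stratum + order fixed | All five fixed |
|---|---|---|---|---|
| Strong | 3 | 68.4% | 73.3% | 77.7% |
| Weak | 3 | 72.9% | 73.9% | 75.7% |
| None | 3 | 74.0% | 73.9% | 72.9% |
| Strong | 5 | 98.5% | 99.0% | 99.5% |
| Weak | 5 | 99.1% | – | 99.3% |
| None | 5 | 99.2% | – | 99.0% |

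Fixing the stratum alone adds little: 68.4% to 69.6% in the strong case at 3 points.

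**Sensitivity to the threshold.** In a separate run of 5,000 trials per cell, the screen was changed to a standardised difference above 0.1. Strong-case power at 3 points was then 73.2%, against 69.7% with p < 0.05 and 78.3% with all five fixed. The shortfall falls from 8.6 to 5.1 points. In the weak case the figures are 74.9%, 73.4% and 76.8%, and the shortfall falls from 3.4 to 1.9.

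**Room for choice.** Reporting the most favourable of four covariate sets (screen, stratum, stratum plus order, all five) gave 8.3% false positives in the strong case. This illustrates an open rule and does not allege intent.

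**PAP-hours model.** Assumed: no true effect, Group 1 hours with mean 4.5 and SD 2, Group 2 at zero, 6,000 trials per cell.

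| Covariates related to hours | False positives, screen | False positives, always adjusted |
|---|---|---|
| One, r = 0.2 | 4.7% | 4.9% |
| One, r = 0.3 | 5.9% | 5.0% |
| Three, r = 0.3, R² 0.02 each | 16.6% | 5.1% |

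The last column is close to 5% because every simulated confounder is on the adjusted list. A real list removes only the confounding due to its own members.

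**The case against.** **The sentence is not exclusive.** It says that unbalanced variables will be used and does not bar others, and the front summary allows for further covariates. This is correct, so a reader should not infer that the plan forbids other covariates. What stands is that imbalance is the only stated trigger, and that an unnamed set of covariates assures neither stratum nor order.

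**The simulated screen is not the plan's.** The p < 0.05 trigger, the prognostic strengths and the 3-point effect are all assumptions. An order effect of ±2 is a 4-point contrast, close to the planned treatment effect. A looser trigger narrows the gap by about 40%. This limits the size; the direction stays unless nothing is prognostic.

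**The sentence may not reach the PAP-hours model.** Its reference to randomisation points to the Group comparison. Since it follows the PAP-hours sentence and speaks of the analyses generally, the wider reading is likely but not certain. On the narrower reading, the PAP-hours model has no stated adjustment beyond baseline.

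**The arm-dependent exclusion.** Section 4.2 says certain extreme-OSA subjects "will be excluded unless they are randomized to immediate PAP arm", and section 13 says such findings "will also result in study exclusion unless they are randomized to expedited PAP arm". A reader might infer that adjusting for the stratum cures the resulting imbalance. It does not. If the subjects lost from Group 2 are assumed to score a further 3 points lower, losing 10, 20 or 40% of that group's RDI ≥30 subjects leaves a bias of −0.10, −0.19 or −0.31 points with the stratum fixed. Under the screen the bias is −0.17, −0.36 or −0.69, so about half remains. The loss shares are unknown. This is a separate issue.

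**Conclusion.** The criterion is wrong and worth replacing, but the consequence for the Group comparison is modest. It amounts to a slightly conservative test, some lost precision if stratum, order or other factors predict the Month 3 score beyond baseline, and an undefined choice of model.

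Two stronger inferences are not supported. A screen fixed in advance does not inflate type I error in the Group comparison; it was at or slightly below 5% in the simulations. Power at the planned 5 points is not materially harmed: the largest change is from 98.5% to 99.5%. The gains at 3 points, from nil to about 9 points, rest on assumed strengths and an assumed trigger.

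For the PAP-hours model, if the sentence governs it, a between-group check cannot find variables related to hours within Group 1, and confounding can remain. Its size cannot be known from the documents. The 16.6% is one illustration among several and should not be quoted as an estimate.

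**What to change.** Before any comparison of outcomes by group, replace the imbalance sentence in section 9.2 with two fixed lists.

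- **Group model:** Group, baseline score of the same test, RDI stratum (<30 or ≥30), and battery order for tests with alternate forms in Table 2. The sponsor may add a short list of prognostic variables already collected, for example age, NAART and self-reported EDSS. All terms enter whatever the observed balance. The imbalance-driven model may stay as a sensitivity analysis only.
- **PAP-hours model:** its own list of baseline variables that could relate to both PAP use and cognition, for example RDI, ESS, ISI, FSS, age and EDSS, besides the baseline score. Label the result a non-randomised association. The Group list will not do here, since a randomised battery order does not confound hours of use.

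Match the front summary to the new wording.

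The cost is a few sentences. All the variables are already collected or generated under sections 6.1 to 6.3. With five added terms and nothing prognostic, mean SE rises from 1.149 to 1.161 and power at 3 points falls from 74.0% to 72.9%. Stratum and order alone cost about 0.1 point.

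Separately, sections 1.3, 4.2 and 13 describe the extreme-OSA exclusion differently: section 1.3 omits the exception for the immediate PAP arm and words the criteria differently. These passages must be reconciled, because covariate adjustment does not resolve them.

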9.3 Analysis of exploratory endpoints

Multiple linear regression models will be used to assess the effect of PAP treatment effect (Group 1 vs. Group 2 effect) on tertiary outcome measures including daytime sleepiness (ESS scores), fatigue (FSS, PROMIS scores), and anxiety, pain, and quality of life (PROMIS scores).

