PAP Therapy: There may be skin irritation related to the **PAP** mask, and masks can be uncomfortable and create a feeling of claustrophobia. There are multiple choices and sizes for sleep masks, and the provider will work with the subjects to find the most comfortable mask. There may be difficulty tolerating the forced air, but the pressure settings can be adjusted by working with the sleep machine provider. Subjects might experience a dry stuffy nose which can be treated with a saline nasal spray or humidified air that can be run through the PAP machine. The providers of these machines are very familiar with resolutions to and they will try and assist subjects in order to resolve any issues.

Confidentiality: The records of this study will remain confidential and protected; however, there is a risk for a breach of confidentiality. This risk is minimal, because a number of precautions have been taken in order to protect confidentiality. All data collected will be kept secure and in a locked office. Records will be coded and identifying information (such as name and registration numbers) will be removed and stored on a key in a separate location so that confidential information cannot be traced back to the subject. Only authorized members of the research team will have access to study records.

Standard care PAP treatment arm (for Group 2): Given that most consequences of OSA take months to years to manifest (cardiovascular disease, metabolic syndrome), we do not anticipate any significant long-term side effects from deferring PAP for 3 months for Group 2. Identification of sleep disordered breathing will be facilitated by enrollment into this study. Nonetheless, to avoid hazardous short-term consequences of OSA caused by excessive

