sleepiness (e.g., motor vehicle accidents), ESS scores ≥ 16 on baseline or follow-up visits will be cause for study exclusion/discontinuation. This cutoff was chosen based on data that demonstrate an ordinal increase in risk of sleepy driving accidents with increases in ESS score, particularly in subjects with ESS scores > 15 . We will also consider extreme OSA (RDI >60 respiratory events per hour, or unstable ECG rhythms on PSG) to be exclusionary, regardless of ESS score. For subjects who are not considered to be high risk per these criteria, we do not expect the risk of participating in this trial and having no CPAP for 3 months to exceed the risk encountered in routine clinical practice, as wait times for sleep clinic evaluations, subsequent sleep clinic referral, PSG, CPAP titration, and CPAP initiation at home currently often amount to 3 months or longer at U-M sleep clinics.

Alternative treatments and procedures: This study does not include an intervention. Therefore, there are no applicable alternative treatments or procedures.

As with any research study, there may be additional risks that are unforeseeable.

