6.6 Month 1 and Month 2 Follow-up Visits/Assessments

Group 1: 1 and 2 months following PAP initiation – *Group 1 subjects will have the option of doing their MONTH 2 assessment by phone or in person*

Group 2: 1 and 2 months following randomization – *Group 2 subjects will have the option of doing either of these assessments by phone or in person*

All randomized subjects will undergo the following assessments:

- 1) Focused medical and surgical history as it relates to MS, sleep, and cardiopulmonary history
- 2) Medication review
- 3) PAP compliance review (datacard assessment) for Group 1
- 4) Fatigue, insomnia, and sleepiness assessments (see 7.2)
- 5) AE/SAE review

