6.7 Month 3 Visit with repeat Cognitive Testing

Group 1: 3 months after PAP initiation

Group 2: 3 months after randomization

All randomized subjects will undergo the following assessments:

- 1) Focused medical and surgical history as it relates to MS, sleep, and cardiopulmonary history
- 2) Medication review
- 3) PAP compliance review for Group 1
- 4) Fatigue, insomnia, and sleepiness assessments (see 7.2)

- 5) Pain, anxiety, and quality of life assessments (see 7.2)
- 6) AE/SAE review
- 7) Repeat neuropsychological testing (see 6.2)
- 8) PAP titration for group 2 (if applicable)*

* Group 2 subjects are encouraged to undergo PAP titration on the night of the Month 3 visit. If they agree to this approach, the PAP titration will be scheduled around the time of the Month 2 visit.

6.8 Post-Study Follow-up phone assessment for Group 2 (1 month after Month 3 visit)

Following the Month 3 visit (and once the PAP titration is complete) , for Group 2 subjects who still express a desire to proceed with PAP treatment, the study team will contact the subject and/or DME company (phone or email) to confirm that a PAP prescription has been faxed to the subject's designated DME company), and if applicable, that UM sleep clinic follow up has been made. Three phone contacts will be attempted. Any barriers to the PAP prescription process will be passed on to sleep clinic staff for appropriate action. If no clinic follow up has been scheduled per the subject's account (and the subject still desires a sleep clinic appointment), the study team will contact appropriate UM sleep clinic personnel to contact the subject.

SCHEDULE OF ACTIVITIES

Study Activity	Baseline Visit	Baseline PSG visit	Month 0	Month 1	Month 2	Month 3
Demographics	X					
Medical/Surgical History	X			X	X	X
Medication review	X			X	X	X
Height, weight, neck circumference	X					
EDSS self-report	X					
AE/SAE review	X			X	X	X
Baseline neuropsych testing (all subjects)	X					
Repeat neuropsychological testing (OSA subjects)						X
Baseline PSG (all subjects who do not have U-M PSG within the past year)		X				
Randomization (for subjects with OSA on baseline PSG)			X			
PAP titration/prescription for Group 1			X			
PAP compliance review for Group 1				X	X	X
Fatigue (FSS), insomnia (ISI), and sleepiness (ESS) surveys	X			X	X	X
PROMIS/NeuroQOL measures	X					X

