9.0 DATA ANALYSIS/STATISTICAL METHODS

9.1 Sample Size Determination

Estimates (means and standard deviations) are derived from our recent data that evaluated SDMT scores among MS subjects referred for overnight PSG, and previously published interventional studies in that evaluated the effects of medical interventions on components of the MACFIMS in MS patients. We have chosen to focus on SDMT score as the primary outcome variable of interest, as the SDMT encompasses multiple domains of cognitive function, is frequently used in MS clinical studies as a reliable measure of cognitive impairment, and is sensitive to changes in intervention.

Based on a power analysis of two sample means (unequal sample sizes, with 2:1 randomization) with a 0.05 two-sided significance level, and an estimated S.D. of 9, a total sample size of 140 subjects will have an 86.3% power to detect a 5-point difference in SDMT score between groups, on month 3 testing, for hypothesis 2. Similarly, using individual MACFIMS components as outcome variables (in separate models), a multiple linear regression power analysis shows that a sample size of n=140 subjects will yield 88% power to detect an R-square difference of 0.05 for the test predictor of interest (% PAP use per month, as a continuous measure), assuming the R-squared explained by the adjustment variables is at least 0.3.

Although we predict a low dropout rate due to the short duration of the study, if we assume a dropout rate of 15% (10 dropouts per group), we will still have a power of 81.2% power to detect a 5-point difference in SDMT score between groups, on month 3 testing.

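### A follow-up sleepiness rule that the protocol states in one place only would, if followed, bias the Month 3 ESS comparison against PAP and leave the cognitive comparison open to a small bias in either direction

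*Combined protocol and SAP*

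**What the plan says.** Section 1.3, under the heading "Standard care PAP treatment arm (for Group 2"), states that "ESS scores ≥ 16 on baseline or follow-up visits will be cause for study exclusion/discontinuation". Two other places give a narrower rule: exclusion criterion 14 in Section 4.2 and the stopping rules in Section 13 both apply the limit of 16 at baseline and do not mention follow-up.

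ESS is collected in both groups at Months 1 and 2 (Section 6.6: "Fatigue, insomnia, and sleepiness assessments (see 7.2")) and again at Month 3 (Section 6.7). The schedule of activities places "Repeat neuropsychological testing (OSA subjects") at Month 3 only. Group 2 has no PAP until that testing is complete.

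For cognition, Section 9.2 says: "Multivariate linear regression models will be used to test the effects of Group effect on 3-month" scores, controlling for the baseline score and adding predictors that turn out unbalanced between groups. For ESS and the other exploratory outcomes, Section 9.3 says: "Multiple linear regression models will be used to assess the effect of PAP treatment effect (Group 1 vs. Group 2 effect"). It names no covariates.

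On losses, Section 9.1 says only "if we assume a dropout rate of 15% (10 dropouts per group"). Section 13 says of a subject who leaves that "all attempts will be made to exit the patient in accordance with the protocol requirements". The documents define no analysis set, give no missing-data method and do not say whether a discontinued subject returns for Month 3.

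**The concern.** If the follow-up rule operates, it selects subjects after randomisation on a variable that treatment is meant to change. Two ESS readings come before the Month 3 outcome, and a subject who reaches 16 at either one may leave without a Month 3 score. If PAP lowers sleepiness, fewer Group 1 than Group 2 subjects cross the limit. The Group 2 subjects who remain are then less sleepy than the group that was randomised.

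For ESS this is selection on the outcome itself, measured at earlier visits. Neither the baseline score nor baseline predictors found to be unbalanced can remove it, because the selection acts on later scores. For the Symbol Digit Modalities Test (SDMT), which Section 9.1 names as the main outcome, the effect depends on how sleepiness, PAP response and cognition are related.

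**Working it through.** **The plan's own figures.** Section 9.1 uses SD 9, a 5-point SDMT difference, two-sided 0.05 and 93 versus 47 subjects. The standard error is 9 × √(1/93 + 1/47) = 1.611, and 5/1.611 = 3.10. Power is Φ(3.10 − 1.96) = 87.4% by the normal formula and 86.9% by the t-test, against 86.3% stated. After dropout, 80 versus 40 gives 81.2% by the t-test, as stated. Taking off 10 per group literally (83 versus 37) gives 79.6%. This allowance covers numbers lost, not who is lost.

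**Inputs for the selection check.** The documents give no ESS mean, SD, retest reliability or PAP effect, so all of these are assumptions. Set A: mean 8 to 10, SD 4 to 5, reliability 0.7 to 0.9, PAP lowers ESS by 2 or 3 points (16 settings). Set B: mean 8 to 12, SD 4.5, correlation between visits 0.75, PAP lowers ESS by 2 or 3 points in responders, with all or half of Group 1 responding.

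**Method.** Each ESS score is a stable subject level plus visit error, less the PAP effect at follow-up visits in Group 1, rounded and held to 0–24. Subjects enter with baseline ESS below 16, are allocated 2:1, and are removed if ESS is 16 or more at Month 1 or 2. The Month 3 score is regressed on group and its baseline value, once in everyone and once in those remaining. The difference between the two group coefficients is the bias.

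**Losses, set A, all responding.** Group 2 loses 2.0% to 13.0% (0.020 × 47 = 0.9 to 0.130 × 47 = 6.1 subjects). Group 1 loses 0.0% to 5.1% (0 to 0.051 × 93 = 4.7). At most that is 6.1 + 4.7 = 10.8 of 140, or 7.7%, which is inside the 15% allowance. In set B, Group 2 loses about 5% to 17%. Group 1 loses about 1% to 6% if all respond and 3% to 12% if half do.

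**ESS effect, rule applied in both groups.**

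| Setting | Everyone | Remaining | Understatement |
|---|---|---|---|
| Set A, largest in points (mean 10, SD 5, reliability 0.7, effect 3) | −2.84 | −2.58 | 0.26 (9%) |
| Set A, largest in per cent (same, effect 2) | −1.91 | −1.72 | 0.19 (10%) |
| Set A, smallest (mean 8, SD 4, reliability 0.9) | | | 0.03 (about 1%) |
| Set B, mean 12, effect 2, all responding | −1.97 | −1.75 | 0.22 (11%) |
| Set B, mean 8, effect 3, half responding | −1.38 | −1.36 | 0.02 (about 2%) |

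With half of Group 1 responding in set A, the effect is understated in 15 of 16 settings and essentially unbiased in the other. With no PAP effect on ESS the bias is zero.

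**If the rule applies to Group 2 only**, as its heading could suggest, Group 2 looks less sleepy even when PAP does nothing. The bias against PAP is then 0.03 to 0.32 points, and the two-sided type I error is 5.1% to 7.8%.

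**SDMT effect, true value 5.** For set A, an SD of 9 and a pre–post correlation of 0.8 (assumed) are used.

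- Uniform response, ESS and Month 3 SDMT unrelated given baseline: 5.0, no bias.
- Uniform response, correlation −0.2 to −0.4: 4.96 to 4.70, an understatement of up to 0.30/5 = 6%. Set B gives up to about 4%.
- Half of Group 1 responding, with the SDMT gain confined to responders (mean 10, SD 5, reliability 0.7, effect 3): 5.28, 5.21 and 5.13 at correlations 0, −0.2 and −0.4. The rule now removes mainly non-responders from Group 1. Set B gives 1% to 8% overstatement; its largest case is 4.99 becoming 5.38.
- 70% responding: about 5.2, 5.06 and 4.98 at the same correlations, so the sign can change within a plausible range.

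**The case against.** The strongest reply is that the rule may not be in force. The sections that would normally govern conduct, the exclusion criteria and Section 13, confine it to baseline, and only the risk discussion in Section 1.3 extends it to follow-up. Section 1.3 also departs from those sections on extreme apnoea, where they exempt the immediate-PAP arm and it does not, so it cannot simply be taken as controlling. Under Section 13 as written, nobody is removed for a follow-up score and there is no bias. This stands, and it makes the point conditional. It does not dispose of it, because Section 1.3 offers the follow-up rule as a safeguard for deferring PAP and nothing withdraws it.

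Second, an analysis of remaining subjects only is an inference. Section 6.7 lists Month 3 assessments, cognitive testing included, for all randomised subjects, and being a cause for discontinuation does not mean exclusion from analysis. That is fair. Still, nothing says that a discontinued subject is tested, and a regression on Month 3 scores with no missing-data method will ordinarily use those who have them.

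Third, a reader might infer that the models adjust for baseline alone. They do not: Section 9.2 adds unbalanced predictors, the synopsis mentions other covariates, and Section 9.3 names no baseline term. None of these addresses selection after randomisation.

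Fourth, the ESS endpoint is exploratory, has no power claim, and shifts by at most about a quarter of a point in set A with the rule in both groups. This is why the point is minor.

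**Conclusion.** The point holds conditionally and is minor. The protocol contradicts itself on whether a follow-up ESS of 16 or more ends participation. If it does, and Month 3 ESS is analysed in those remaining, the PAP effect on sleepiness is understated by roughly 0 to 10%, reaching 11% at an assumed ESS mean of 12. This requires that PAP lowers ESS; if it does not and the rule covers both groups, there is no bias.

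A reader might go further and conclude that the plan understates the PAP effect on cognition. The documents do not support that. The SDMT bias is near zero if ESS and SDMT are unrelated and response is uniform, downward if they are linked and response is uniform, and upward if the rule mainly removes PAP non-responders. Section 9.2 itself models hours of PAP use, so uniform response cannot be presumed. All sizes rest on assumed ESS inputs.

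**What to change.** 1. Make Section 1.3, exclusion criterion 14 and Section 13 agree on whether the follow-up rule applies, and to which groups.
2. If it applies, state in Sections 6.7 and 13 that discontinued subjects are still asked to attend the scheduled Month 3 assessment and are analysed as randomised. Record any PAP started before Month 3 in Group 2, since an as-randomised comparison will include its effect.
3. In Section 9.3, analyse ESS at Months 1, 2 and 3 in one repeated-measures model with baseline ESS, group, visit and group by visit, and report the Month 3 contrast. The score that triggers removal is then part of the analysis.
4. As a sensitivity analysis for Section 9.2, multiply impute missing Month 3 cognitive scores within group from the baseline score and from baseline, Month 1 and Month 2 ESS. It should not replace the main analysis: it targets a hypothetical effect without early discontinuation and adds modelling assumptions with about 47 subjects in Group 2. In simulation, imputation from the interim ESS scores brought the ESS and SDMT effects to within 0.01 of the full-data result, but the simulated data had nearly the form that the imputation assumes.
5. Report by group how many subjects reach 16 at follow-up.

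The cost is a few sentences, one table, a little more analysis and continued Month 3 contact with discontinued subjects. The models use ESS scores already scheduled for collection. If few subjects reach 16, the correction will be small.
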